We considered a host of potential moderators on which to stratify randomization, but ultimately the sample size should be sufficient to equalize groups (if incorrect, analyses will include covariates). However, outcomes might very well be moderated by readiness to quit, and thus randomization will be stratified based on desire to quit in next 30 days (0-6 vs. 7-10 on a VAS scale). We will also stratify on locally recruited vs. not. Participants will be randomized via a stratified, mixed block design, overseen by our statistician.

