One clear advantage of NJoy system is that is the basis for the newly released NIDA Standardized Research E-Cigarette (SREC), which now provides a naturalistic test of a standardized product that will be used in other lab-based studies (<http://www.e-cigarette-summit.us.com/files/2017/05/Kevin-Walton.pdf>). In fact the only difference between our product and the SREC will be packaging; ours will be provided in original NJOY packaging. A menu of several e-cigarette products would better reflect our naturalistic intent, but this would introduce too much variability, as we would need to account for switching between products and a range of product characteristics. While this study is based on one product alone, we view it as a test of the concept of e-cigarettes in general, and thus more broadly generalizable. We recognize that products change regularly and what we choose now may not be the best option once this study starts. There are other options that may meet our criteria (e.g., V2, LogicPro) and if a more efficient, closed tank-based system becomes available, we will

consider it. Throughout this decision process, we will work within our investigative team prior to study onset to verify product and will discuss changes with NIH. NJoy availability or design might also change after the study starts, and if so the same guiding principles will apply. We expect product changes during the course of the study, as occurred within our R21. We view this as a strength, not a weakness, in that a) it gives us an opportunity to inventory a small number of each product for lab testing and product comparison, b) allows us to examine product evolution over time, and c) allows for sub-analyses of each product, recognizing limited power to do so. The overall comparison of e-cigarette vs. control group will control for any product changes as a covariate. Finally, to **authenticate key biological variables**, we will verify the nicotine content (through sub-contract with [name]) on a regular basis (e.g., xx times per year, or every Nth product; depending on participant flow).

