All analyses are based on an intent-to-treat approach, and are nearly identical to analyses from our prior studies. Exploratory analysis will be performed on all outcomes, and both graphical displays and summary statistics will help determine if transformations will be needed. Any significant baseline differences between groups will be included in regression analyses described below. Missing Data: The most conservative approach for handling missing data (136) is to substitute them with baseline values, assuming outcomes have all returned to baseline, with no quit attempts made. If this assumption is incorrect, it biases the results towards the null by reducing between group differences (136). SRNT recommendations (136) suggest that when there are small amounts of missing data (< 10%) the conservative approach can be used with little bias in outcome. If missing data >10%, we will calculate results not only using this conservative method but also using methods in which missing data are imputed as described in the SRNT guidelines. We will also assess whether dropout is differential by study group. In our current and recent studies of cessation induction, this has not been the case, and we expect similar results here. Finally, though sex/gender is not an explicit focus, we are well poised, given our sample size, to address **potential sex/gender influences** on study outcomes.

Hyp 1a: Within the e-cigarette group, we hypothesize that at least 90% of smokers will try at least once, 45% will use regularly (at least 4/7 days, at any time during follow-up), 25% will use daily for ≥ 7 days (at any time during follow-up), 25%/10% will be using at least some/daily at final follow-up, and 20% will independently purchase e-cigarettes. Within the e-cigarette group (N=440), we will analyze prevalence of each definition of uptake. We will estimate each of these parameters, and the 95% confidence interval for each proportion.

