Hyp 3: Provision and use of e-cigarettes will lead to increased incidence of (Hyp3a) quit attempts, (Hyp 3b) cessation, and (Hyp 3c) motivation/confidence to quit. Logistic regression analyses will be performed with (1) any quit attempt [QA] within 6 months (1=one or more quit attempts, 0=none), (2) any 24hr QA (same), (3) point prevalence abstinence at 6 months (1=7 day abstinence at 6 months, 0=not abstinent), and (4) floating abstinence (1=any 7 day period of abstinence during study, 0=no abstinence) as the outcomes and group (e-cigarette vs. control) as the covariate. The coefficient on group provides a log odds ratio for measuring the odds of (1) any self-defined QA's, (2) 24hr QA's, (3) point prevalence abstinence, and (4) floating abstinence. Statistical significance of these coefficients will be assessed using a p-value with a two-sided $\alpha=0.05$, and both the odds ratio and its 95% confidence interval (CI) will be reported. Motivation and confidence to quit are evaluated on a continuous scale (0-10), and linear regression models will be used for both, with group (e-cigarette vs. control) as the covariate (along with any other baseline differences as covariates). To fully capitalize on the longitudinal nature of our data, secondary analyses will include a) regression analyses where number of QA's are compared across groups using poisson or linear regression (depending on the distribution of QA's), b) latency to any quit attempt, and c) stability of e- and conventional cigarette use over time. We will also repeat above analyses: a) based on those who do vs. do not use e-cigarettes, and b) using quit attempts and abstinence of all tobacco products, including e-cigarettes.

Ancillary Analyses:

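### The between-group analyses leave out the randomisation strata, choose covariates by baseline significance, and promise a product-change covariate that has no definition in the control arm

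*Combined protocol and SAP*

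**What the plan says.** **Randomisation.** The Randomization section says "thus randomization will be stratified based on desire to quit in next 30 days" (0-6 versus 7-10), because readiness to quit may moderate outcomes. It adds "We will also stratify on locally recruited vs. not". For everything else it expects that "the sample size should be sufficient to equalize groups (if incorrect, analyses will include covariates").

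**Models.** Under Statistical Considerations – Data Analyses, Hyp 1b is a plain chi-square test and Hyp 2 uses two-sample t-tests and two one-sided equivalence tests. The Hyp 3 logistic models take their endpoints "as the outcomes and group (e-cigarette vs. control) as the covariate". The Data Analysis Plan in the Data and Safety Monitoring Plan repeats these analyses, and neither version names a stratum.

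**Covariates.** The Data Analyses section sets one general rule: "Any significant baseline differences between groups will be included in regression analyses described below". For motivation and confidence (Hyp 3c) that section lists group, "along with any other baseline differences as covariates". The monitoring plan's version of the same model also fixes the baseline score as a covariate.

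**Product changes.** The E-cigarette Group section says "We expect product changes during the course of the study, as occurred within our R21" and then "The overall comparison of e-cigarette vs. control group will control for any product changes as a covariate". The Control Group section makes group assignment, not product use, the independent variable in the primary analyses. Neither description of the Hyp 3 models contains a product term.

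**The concern.** There are two separate gaps.

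First, the design singles out desire to quit as likely to matter and balances on it, but the analysis does not use it. The significance rule cannot be relied on to bring it back, because it responds to chance imbalance and stratified blocks remove most of that. The covariate set also stays open until the groups have been compared.

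Second, a covariate for product version exists in one arm only. With an intercept, a group term and an indicator for each of two versions, the design matrix has rank 3 of 4, so a separate no-product level for controls cannot be estimated alongside group. Some other coding has to be chosen, and the plan does not choose one. A natural choice sets controls to the reference version. The group coefficient then compares that version alone with control, which is not the comparison by assignment that the Control Group section calls primary.

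At stake are the estimand and power for six-month abstinence, the endpoint on which the trial is powered.

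**Working it through.** **The plan's own figure.** Inputs from the sample size section: 8% versus 16%, 2:1 allocation, two-sided 0.05, 80% power, chi-square test. The pooled rate is (0.08 + 2 × 0.16)/3 = 0.1333. Controls needed:

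[1.960 × √(1.5 × 0.1333 × 0.8667) + 0.8416 × √(0.0736 + 0.1344/2)]² / 0.08² = (0.8160 + 0.3158)² / 0.0064 = 200.15

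This rounds up to 201, or 603 in total, against 600 stated. With 200 versus 400 the power is 0.7997. The figure reproduces, and it is based on an unadjusted test.

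**Strata.** Assumptions not in the documents: 40% in the high-desire stratum, 2:1 within strata, and a common conditional odds ratio (OR) solved to give 16% overall. The tests are Pearson chi-square and Cochran-Mantel-Haenszel, with 200,000 replicates.

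| Control rate, low/high desire | Conditional OR | Power, unadjusted | Power, stratified | Gain (points) | Type I error, unadjusted |
|---|---|---|---|---|---|
| 6% / 11% | 2.21 | 0.809 | 0.812 | 0.3 | 0.049 |
| 4% / 14% | 2.27 | 0.812 | 0.827 | 1.5 | 0.047 |
| 2% / 17% (extreme) | 2.40 | 0.818 | 0.852 | 3.4 | 0.042 |

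A second set-up (N = 660, logistic models, conditional OR fixed at 2.19) gave gains from none to about 4 points.

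**Significance rule.** The chance that at least one of k independent baseline variables enters is 1 − 0.95^k, which is 23%, 40% and 54% for k = 5, 10 and 15. In simulation with 10 variables, one of them prognostic, type I error was 0.048 with or without the rule. At a log OR of 1.0 per SD, power was 0.80 unadjusted, 0.80 under the rule and 0.85 with the variable prespecified. At 0.5 per SD the figures were 0.80, 0.80 and 0.81. The desire-to-quit stratifier was selected in 0 of 5,000 randomisations under each of four block schemes. The largest chi-square was 0.29, against a critical value of 3.84.

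**Product term, equally effective versions.** All e-cigarette participants are taken to quit at 16%. The OR is (0.16/0.84)/(0.08/0.92) = 2.19 under any coding, but with reference coding only holders of the reference version inform the group term. Its standard error is √[1/(0.16n) + 1/(0.84n) + 1/16 + 1/184], where n is the number holding the reference version.

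| Share on reference version | n | SE of log OR | Power (Wald, simulated) |
|---|---|---|---|
| No product term | 400 | 0.294 | 0.80 |
| 75% | 300 | 0.305 | 0.76 |
| 50% | 200 | 0.324 | 0.70 |
| 25% | 100 | 0.377 | 0.54 |

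Chi-square gives 0.77, 0.70 and 0.56 for the last three rows. Logistic simulation at N = 660 shows the same pattern: about 81%, 73% and 59%, against 83-84% with enrolment period coded in both arms and 85-86% with no product term. At 200 versus 400, period coding gives 0.807 (Cochran-Mantel-Haenszel) and no product term 0.806 (Pearson), so period coding costs and gains essentially nothing.

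**Product term, unequal versions.** Suppose half the arm holds a 16% version and half a 12% version, so 14% overall. The overall OR is (0.14/0.86)/(0.08/0.92) = 1.87. With the 16% version as reference, the group term is 2.19.

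**The case against.** The product-term harm needs three things together: an actual change, the term in the operative model, and reference coding. The documents expect changes but record none, and the version dated 11-1-2021 still names one product line. The Hyp 3 models carry no product term. Period coding in both arms is an equally available reading and does no harm. All of this stands, and it reduces the point to an unreconciled sentence with a possible cost.

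A reader might infer a much larger effect. With versions at 12% and 20%, half the arm each, reference coding gives an OR of 1.57 or 2.88 (power 0.26 or 0.94) around an overall 2.19. That needs an 8-point gap between versions, as large as the whole effect the trial is powered on, and nothing in the documents supports it.

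A reader might also infer that the tests are invalid. They are not: omitting the strata makes them slightly conservative, the power calculation is itself unadjusted, and the significance rule showed no type I inflation. The stated reason for stratifying is moderation, and the Moderator analyses do list motivation to quit. This softens the strata point, but that list is optional and does not put the stratum in the main comparison.

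Finally, the Quality Assurance Plan mentions follow-up rates and extra-study cessation treatment as things that analyses might need to be adjusted for. A reader might take this as planned adjustment for post-randomisation variables. It is a conditional data check, and the Hyp 3 models do not include them.

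**Conclusion.** The point holds as a low-cost improvement to the specification, not as an error that invalidates the trial.

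- Strata: about 0.3 to 1.5 power points in moderate scenarios and 3.4 in an extreme one, where unadjusted type I error is 0.042. This rests on an assumed 40% high-desire share and assumed stratum rates.
- Product term: the commitment to adjust conflicts with the stated models and with analysis by assignment. If a change occurs and controls sit at a reference version, power falls to 0.76, 0.70 or 0.54 at reference shares of 75%, 50% or 25%, even with equal versions. If versions differ, the OR depends on the reference chosen. The shares are assumptions.
- Significance rule: it forgoes the precision of planned covariates and leaves the model open, without measurable harm to type I error.
- Hyp 3c: the two descriptions differ on the baseline score and need aligning.

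The primary uptake outcome is estimated within the e-cigarette arm and is untouched. The 600/660 sample size does not change.

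**What to change.** 1. Include desire to quit and local/national, as randomised, in every full-sample between-group model, and desire to quit alone in the local subset. As randomised matters because the section on enrolling sites moves Charleston recruits without a baseline lab visit to the national count. Name the strata-adjusted estimate as primary, and report the unadjusted risk difference as supportive. The order must be stated because adjustment turns the marginal OR (2.19) into a conditional one (2.21 to 2.40 in the scenarios above).
2. Reconcile the product-change sentence with the Control Group and Hyp 3 text. Either drop the term from the overall comparison or replace it with enrolment period defined in both arms. Keep product version for analyses within the e-cigarette arm.
3. Include baseline motivation or confidence in the Hyp 3c models in both places.
4. Replace the baseline-significance rule with a short prespecified list of baseline covariates.
5. As a minor clarification, state that post-randomisation variables such as extra-study cessation treatment stay out of the primary models.

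The cost is analysis-plan wording, a few lines of code and one extra reported estimate. Strata, baseline scores and enrolment dates are already collected.

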Assessments will occur at 7 points: baseline, weekly x4 for first month, and at both 3 and 6 months. Our baseline demographic questionnaire will include common items from NHIS and Adult Tobacco Survey. We will assess prior quit history (#, duration of attempts, medications used), motivation to quit, dependence, using standardized surveys were possible (110-113). We also assess withdrawal (114), and attitudes towards novel products (115-119). Follow-up assessments (~20-25min phone call, based on our prior experience) include:

Uptake Based in part on marketing theory that describes product adoption/diffusion (120), we will report incidence rates for uptake of use, based on participants who engage in: a) first time use, b) repeat use, c) first time buyer, d) repeat buyer, and e) advocacy; i.e., promoting/suggesting to others. We will also be poised to assess the time course for each. We will also track transitions to other e-cigarette systems, e.g., tanks, flavors.

Patterns of E-Cigarette Use Through both diaries and phone-based assessments, we will determine the duration, quantity, and frequency of e-cigarette use, as well ascertain the context in which it is used (e.g., places with smoking restrictions vs. other) using prior methods (121). We will specifically ask if e-cigarettes are used “not to quit, but to reduce the amount you smoke” or “not to quit or reduce smoking, but to get you through times when you cannot smoke.” Some research (122) suggests a distinction between purpose-driven use vs. mere experimentation, with different trajectories/consequences of each, and we will assess this as well. We will also assess any use of other tobacco products, and can determine patterns of dual use as well.

Other e-cigarette outcomes We will also assess likeability/preference of e-cigarettes through items derived from the Cigarette Evaluation Scale (123) and related acute effects from smoking (e.g., calming, relaxing, arousing) (124), and select items from the Product Evaluation Scale (125) that is specifically meant for evaluation

of novel products. Lastly, though assessment of e-cigarette dependence is not well understood (126), we will use the recently developed scale from Foulds et al (127).

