Hyp 3: Provision and use of e-cigarettes will lead to increased incidence of (Hyp3a) quit attempts, (Hyp 3b) cessation, and (Hyp 3c) motivation/confidence to quit. Logistic regression analyses will be performed with (1) any quit attempt within 6 months (1=one or more quit attempts, 0=none), (2) any 24hr quit attempt (1=one or more 24 hour quit attempt, 0=none), (3) point prevalence abstinence at 6 months (1=7 day abstinence at 6 month call, 0=not abstinent), and (4) floating abstinence (1=any 7 day period of abstinence during study, 0=no abstinence) as the outcomes and group (e-cigarette vs. control) as the covariate. The coefficient on group provides a log odds ratio for measuring the increased odds of (1) any self-defined quit attempts, (2) 24hr quit attempts, (3) point prevalence abstinence, and (4) floating abstinence in the e-cigarette group compared to the control group. Statistical significance of these coefficients will be assessed using a p-value with a two-sided alpha of 0.05, and both the odds ratio and its 95% confidence interval (CI) will be reported. Motivation and confidence to quit are evaluated on a continuous scale (0-10), and linear regression models will be used with motivation/confidence to quit at 6 months as the outcomes with group (e-cigarette vs. control) as the covariate (along with baseline motivation/confidence and any other variables that are different between groups at baseline treated as covariates). Secondary analyses will include regression analyses where number of quit attempts are compared across groups using poisson or linear regression (depending on the distribution of number of quit attempts). We will also repeat this analysis: a) based on those who do vs. do not use e-cigarettes, and b) using quit attempts and abstinence of all tobacco products, including e-cigarettes.

10. Quality Assurance Plan

The REDCap system has validation options to not accept outliers, illogical response patterns, etc. The PI will have weekly meetings with the research assistants to discuss qualitative comments received during data collection and any problems in data collection. The statistician will periodically examine the database to look for irregularities. Initial data analyses will examine distributions of variable scores, comparability of baseline characteristics, follow-up rates and use of extra-study cessation treatment across conditions in case analyses need to be adjusted for these.

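### Hyp 3c (motivation and confidence to quit) has two differently worded models; only one always adjusts for the baseline score, and nothing says which governs

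*Combined protocol and SAP*

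**What the plan says.** Hyp 3c is one of three hypotheses under Aim 3. Its analysis is described twice.

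- **Statistical Considerations – Data Analyses, Hyp 3.** For motivation and confidence, "linear regression models will be used for both, with group (e-cigarette vs. control) as the covariate (along with any other baseline differences as covariates"). The opening paragraph of that section sets the covariate rule: "Any significant baseline differences between groups will be included in regression analyses described below". The section does not name the baseline score or an outcome time point, and does not say whether the outcome is a level or a change.
- **DSMP, section 9 (Data Analysis Plan), Hyp 3.** The models take "motivation/confidence to quit at 6 months as the outcomes with group (e-cigarette vs. control) as the covariate", and the covariates are given as "along with baseline motivation/confidence and any other variables that are different between groups at baseline treated as covariates".

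Both describe the outcome on the same 0-10 scale: "Motivation and confidence to quit are evaluated on a continuous scale (0-10"). Under Randomization, "randomization will be stratified based on desire to quit in next 30 days (0-6 vs. 7-10 on a VAS scale"), and also on local versus national recruitment. Neither Hyp 3c model names these factors. Under Other Assessments the baseline battery is described as "We will assess prior quit history (#, duration of attempts, medications used), motivation to quit, dependence".

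**The concern.** One named hypothesis has two written models, both in current text, with no order of precedence. They can give different estimates, intervals and p-values, so an analyst could choose between them after seeing the data.

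The gap is wider than one covariate. The plan assesses motivation at every contact and schedules six follow-up calls (+10, +17 and +24 days; 1, 3 and 6 months). Only the DSMP wording fixes the time point.

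The main-section wording also gives up precision if the baseline score predicts the 6-month score. Its rule of adding covariates only when they differ significantly would seldom bring the baseline score back in.

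**Working it through.** **1. The plan's own figure.** The documents give no sample size, power, SD, effect or correlation for Hyp 3c. The available N comes from 6-month abstinence: 8% versus 16%, 2:1, 80% power, two-sided 0.05, stated as 600 (660 after inflation for attrition). The pooled formula without continuity correction, with p̄ = (0.08 + 2 × 0.16)/3 = 0.1333, is

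n(control) = [1.960 × √(1.5 × 0.1333 × 0.8667) + 0.842 × √(0.08 × 0.92 + 0.16 × 0.84/2)]² / 0.08² = (0.816 + 0.316)² / 0.0064, which rounds up to 201.

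The total is 3 × 201 = 603, against 600 stated, so the figure reproduces. I use 200 control and 400 e-cigarette below.

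**2. Group alone, follow-up level as outcome.** Two-sided 0.05 is stated for the Hyp 3 logistic coefficients ("Statistical significance of these coefficients will be assessed using a p-value with a two-sided alpha of 0.05"). I assume that it also applies to the linear models. The effect detectable with 80% power is

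(1.960 + 0.842) × √(1/200 + 1/400) = 2.802 × 0.0866 = 0.243 SD.

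With 220/440 it is 0.231 SD.

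**3. Baseline always included.** With correlation ρ between baseline and 6-month score, the residual SD is multiplied by √(1 − ρ²). At the effect from step 2, power = Φ(2.802/√(1 − ρ²) − 1.960). ρ is an assumption.

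| Assumed ρ | Residual variance | Power, group alone | Power, baseline included | Detectable effect (200/400) | Share of sample lost by omitting baseline (ρ²) |
|---|---|---|---|---|---|
| 0.3 | 0.91 | 80% | 83.6% | 0.231 SD | 9% |
| 0.5 | 0.75 | 80% | 89.9% | 0.210 SD | 25% |
| 0.7 | 0.51 | 80% | 97.5% | 0.173 SD | 49% |

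If the SD is also assumed to be 2.5 points, the detectable difference falls from 0.243 × 2.5 = 0.61 points to 0.210 × 2.5 = 0.53 points at ρ = 0.5.

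**4. Does the adjust-if-different rule recover the loss?** I simulated 200/400 at the step 2 effect, 6,000 runs per setting, adding baseline only if it differed at p < 0.05.

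| Randomization | ρ | Baseline added | Power, adjust if different | Power, always adjust |
|---|---|---|---|---|
| Not stratified | 0.3 / 0.5 / 0.7 | about 5% of trials | 80% / 82% / 82% | 83% / 90% / 97% |
| Stratified on dichotomized baseline | 0.3 / 0.5 / 0.7 | about 0.2% of trials | 81% / 82% / 85% | 83% / 90% / 98% |

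The rule recovers little. With stratification the test without baseline is also conservative: type I error is about 0.04, 0.03 and 0.02 at the three values of ρ. The stratified runs treat the stratifying item as the baseline score itself, which is the strongest case.

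**5. If the main section means a change score.** The SD factor becomes √(2(1 − ρ)), and power at the same effect is 65.8%, 80.0% and 95.1% for ρ = 0.3, 0.5 and 0.7. Each is below the baseline-adjusted figure. The text does not say that change is meant.

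**The case against.** The best defence is that the two texts are one model, written once in full and once in short form. The word *other* in the main section's parenthesis has no referent unless a baseline term is understood, and the DSMP supplies that term. The DSMP repeats the analysis section with small differences elsewhere too: NNAL appears in Hyp 2 of the main section but not in the DSMP version. Since the main section gives no time point, it can hardly be run without the DSMP. This is plausible, but it remains an inference, and if it is right the sentence should simply be completed.

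A reader might infer that the main-section model fails to test an increase, or is biased, because it ignores the starting level. The documents do not support that. Hyp 3c is framed against control, and under randomization the difference in follow-up means estimates the same group effect as a difference in change or a baseline-adjusted difference. Only precision differs. The main section also does not say that it compares levels.

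Nor do the documents show that the baseline score is the strongest predictor available, or that power is in fact lost by a given amount. The correlation, the SD and the 80% starting point are all assumptions. At ρ = 0.3 the gain is only 3.6 percentage points.

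Finally, Hyp 3c is not the primary outcome (uptake) and not the outcome used for sample size (6-month abstinence). That stands, and it keeps the point minor.

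**Conclusion.** The mismatch is real and minor. The main section and DSMP section 9 specify the Hyp 3c analysis differently, and nothing ranks them. The main-section version, taken literally with follow-up level as outcome, is valid but less precise for any non-zero correlation between baseline and 6-month scores.

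The size is conditional. Against 80% under group alone, always adjusting gives about 84%, 90% or 98% power at an assumed correlation of 0.3, 0.5 or 0.7. If stratification on desire to quit already balances the baseline score well, the gain is somewhat smaller: roughly 2, 8 and 13 points in the simulation. The plan's substitution of baseline values for missing follow-up would tend to raise the correlation, and with it the cost of leaving baseline out.

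The sample size of 600, inflated to 660, is unaffected.

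**What to change.** Put one model, in identical words, in both the main analysis section and DSMP section 9:

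- Outcome: the 6-month score, with separate models for motivation and for confidence.
- Terms: group and the baseline value of the same scale, entered regardless of any observed imbalance.
- Optional: the stratification factors (desire to quit 0-6 versus 7-10; local versus national).
- For this analysis, drop the rule of adding covariates because they differ at baseline.

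The last item means that the DSMP wording cannot simply be copied across: it too adds variables that differ between groups, which keeps a data-driven choice. Both sections therefore need an edit.

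The new sentence should also identify the scale. The assessment section measures readiness over both 1 and 6 months, separately for conventional and e-cigarettes.

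The cost is a few lines of wording before analysis, with no new design element. One check is needed: Other Assessments lists motivation at baseline but does not name confidence, while the DSMP model presupposes a baseline value for both. Confirm that baseline confidence is recorded.
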